3.3.1.2 Baseline

For analyses on the full analysis set (FAS) and the safety analysis set (SAS), baseline is defined as the last non-missing value prior to or on the date of study treatment administration including unscheduled assessments that occur prior to first administration of study treatment.

Baseline definition will consider date, and time of data collection (if available). The pre-dose assessment will be used as baseline. If time of first study treatment administration is unavailable, the measurement will be assumed to be pre-dose unless the CSP suggests otherwise. Additionally, if there is only one visit eligible to assess participant status at baseline and it occurs on the date of randomization without a recorded time for the assessment, we should also assume it is a baseline assessment unless the CSP suggests otherwise. If more than one assessment is conducted before the first study treatment

administration, assessment conducted closest to the first study treatment intake will be taken as the baseline value.

If there are more than one assessment that meet the baseline criteria (for example, several assessments on the same date prior to first administration and occurring either at the same time or one or all of them without collected time), the average of these values will be used as a baseline. In case of qualitative variables, the clinically least abnormal value will be taken as the baseline value.

Missing baseline values will not be imputed.

3.3.1.3 Definition of study periods

The following periods are defined in this study:

1. Screening

Start: Signing of the ICF

End: Day prior to first study treatment administration

2. On-treatment period

The on-treatment analysis period starts on the date of the first administration of study treatment and ends on the earliest of 10 days following the date of last dose of study treatment or the end of the on-study analysis period.

Start: Day of first study treatment administration

End: Day of last study treatment dose + 10 days

OR

End of on-study analysis period

Whichever occurs earlier

3. Follow-up period

Start: The day after the end of the treatment period

End: Last day in the study as recorded on the End of Study (EOS) form

4. On-study period

The on-study analysis period starts on the date of the first administration of study treatment and ends on the End of Study date as recorded on the EOS form, unless the participant dies while under follow-up, then the date of death is taken as the end of the on-study analysis period, as reported on the EOS form. No data should be collected after withdrawal of consent. If a participant withdraws consent to continue in the study, then the on-study analysis period ends on this date at the latest.

Start: Day of the first study treatment administration

End: Last day in the study as recorded on the End of Study (EOS) form

The allocation to the study periods is performed after the imputation of date as in Section 3.3.1.6.

3.3.1.4 Intercurrent Events

Intercurrent events (ICEs) are events that happen after treatment initiation and affect either the existence or interpretation of planned measurements.

The intercurrent events, and the applied analysis strategy considered in this SAP are summarized in Table 3.

Table 3– Expected ICEs and the Corresponding Statistical Considerations by Estimand

ICEs	Hypothetical strategy for ICEs defined in the CSP	Treatment policy strategy for ICEs defined in the CSP	Handling in the safety analysis	
			On-treatment	On-study
1. Premature and permanent discontinuation of study treatment	Hypothetical strategy	Treatment policy strategy	Hypothetical strategy	Treatment policy strategy
2. Change in background lipid lowering statin therapy	Hypothetical strategy	Treatment policy strategy	Treatment policy strategy	
3. Initiation, change or discontinuation in non-prohibited background lipid lowering non-statin therapy	Hypothetical strategy	Treatment policy strategy	Treatment policy strategy	
4. (a) Prohibited medication affecting lipid parameters	Hypothetical strategy	Treatment policy strategy	Treatment policy strategy	
(b) Prohibited medication not affecting lipid parameters	Treatment policy strategy		Treatment policy strategy	
5. Any concomitant medication not explicitly specified in the above categories	Treatment policy strategy		Treatment policy strategy	

6. Death	Hypothetical strategy	Hypothetical strategy	Hypothetical strategy	Hypothetical strategy
----------	-----------------------	-----------------------	-----------------------	-----------------------

ICEs – Intercurrent Events

The occurrence of any ICE does not automatically trigger premature and permanent study discontinuation as described in Section 7. of the latest approved CSP. In case of still applying consent, the participants are expected to attend assessments as described in the Schedule of Activities.

The following ICEs are considered:

1 Premature and permanent discontinuation of study treatment

2 Change in background lipid lowering statin therapy

The allowed background lipid lowering statin therapies are described in Appendix F of the last approved version of CSP and the latest approved version of the Statin eligibility memo. Background therapy is recorded in the EDC as prior medication.

Possible mechanisms of change in background lipid lowering statin therapy include:

(a) Discontinue statin therapy

(b) Change to a different statin therapy in the same intensity category

(c) Change between two statin therapy in allowed intensity category

(d) Change the dose of the statin therapy

(e) Change to a statin therapy in a non-allowed intensity category

3 Initiation, change or discontinuation in non-prohibited background lipid lowering non-statin therapy.

Substances to be considered as non-prohibited background lipid lowering non-statin therapies:

(a) Ezetimibe

(b) Bempedoic acid

4 Prohibited medication

Prohibited medications are defined in Section 5 of the latest version of the CSP and the latest approved version of the Protocol Deviation Plan.

Prohibited medication is recorded in the EDC as concomitant medication. Prohibited medication intake will be identified by comparison with the substance list found in the

Appendix of the latest approved Prohibited Medication Memo. In this study we distinguish the prohibited medications according to the following categories:

(a) Prohibited medication affecting lipid parameters

These medications interfere with the interpretation of the efficacy endpoints in the study. As such, their effect on the efficacy endpoints will be investigated according to the ICE handling strategies in [Table 3](#).

(b) Prohibited medication not affecting lipid parameters

These medications do not interfere with the interpretation of the efficacy endpoints in the study. As such, they will be handled with the treatment policy strategy, as defined in [Table 3](#).

5 Any concomitant medication not explicitly specified in the above categories

6 Death

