## Estimand for efficacy endpoints

Intercurrent events (ICE) are events occurring after treatment initiation that affect either the interpretation or the existence of the measurements associated with the clinical question of interest. In this study, ICEs of interest for efficacy evaluation include treatment discontinuation, change in background therapy, and intake of prohibited medication.

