## **6.9 Prior and Concomitant Therapy**

Any medication or vaccine (including over the counter or prescription medicines, recreational drugs, vitamins, and/or herbal supplements) that the participant (except for screen failures) is receiving at the time of enrollment or receives during the study, or other specific categories of interest such as cholesterol lowering therapy within the last 12 months must be recorded along with:

- Reason for use
- Dates of administration including start and end dates
- Dosage information including dose, frequency and route.

Participants will be required to continue on stable doses of their dyslipidemia maintenance therapy (SoC) throughout the study to minimize the risk of disease worsening during the study.

The Study Clinical Lead should be contacted if there are any questions regarding concomitant or prior therapy.

Concomitant medications that contain a black box warning for significant QT prolongation are prohibited within this study.

Fibrate therapy and derivatives are prohibited.

Paracetamol at doses of £ 2 grams/day, is permitted for use any time during the study. Other concomitant medication may be considered on a case-by-case basis by the investigator in consultation with the Study Clinical Lead if required.

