2 CHANGES TO PROTOCOL PLANNED ANALYSES

- ECG parameters will be presented descriptively, treatment emergent abnormalities will be summarized, shift tables will be produced and key subject information will be listed.
- Multiplicity adjustments will not be applied for any of the secondary endpoints, and will have nominal p-values presented only.
- Two subcategories of the intercurrent event ‘change in background therapy’ are introduced:
 - ‘Change in background lipid lowering statin therapy’
 - ‘Initiation, change or discontinuation in non-prohibited background lipid lowering non-statin therapy’ to account for non-statin therapies (such as ezetimibe and bempedoic acid) when assessing the treatment effects.
- The ICE ‘Prohibited medication intake’ is clarified as ‘intake of prohibited medication affecting lipid parameters’.
- Addition of the ICE ‘Prohibited medication not affecting lipid parameters’, ‘intake of any other concomitant medication’, and ‘death’.

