4.1.8 Prior and Concomitant Medications

4.1.8.1 Definitions and Derivations

Prior medications are those taken prior to study treatment with a stop date prior to the first dose of the study treatment.

Concomitant medications (CM) are either ongoing or those with a stop date on or after the date of the first dose of study treatment, and must have started prior to or during treatment so there is at least one day in common with the study treatment.

Prohibited concomitant medications are defined in Section 5. and 6.9 of the CSP, and are listed in the latest approved version of the Prohibited Medication Memo. All other concomitant medications are classified as allowed.

Prior and concomitant medications will be coded according to WHODrug.

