4.2.1 Primary Endpoint

4.2.1.1 Definition

The primary efficacy endpoint is percent change from baseline to Week 12 in direct LDL-C. The clinical question of interest is:

What is the difference in means of percent change in LDL-C from baseline to Week 12 in participants with dyslipidemia treated with AZD0780 vs placebo in the hypothetical condition that all participants could adhere to study intervention and non-prohibited

background lipid lowering statin and non-statin therapy, prohibited medications affecting lipid parameters were not available, regardless of whether additional treatment is used, where participants cannot die.

The primary estimand attributes are defined as:

- Treatment: AZD0780 or placebo.
- Population: Male and female participants of non-childbearing potential, 18 to 75 years of age with dyslipidemia, defined by the inclusion and exclusion criteria. Implemented using FAS.
- Endpoint: Percent change in direct LDL-C from baseline at Week 12.
- Population-level summary measure: Difference in means of percent change in direct LDL-C from baseline to Week 12 between AZD0780 and placebo.
- Handling of intercurrent event: The hypothetical strategy will be used for premature and permanent discontinuation of study treatment; change in background lipid lowering statin therapy; initiation, change or discontinuation in non-prohibited background lipid lowering non-statin therapy and intake of prohibited medications affecting lipid parameters. Efficacy assessments obtained after these will not be included in the analysis. Initiation or changes in other concomitant or prohibited medication will be handled with treatment policy strategy. Deaths will be handled with a hypothetical strategy.

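### SAP 3.3.1.4 closes the non-statin background list at two drugs, so any other unlisted lipid-lowering drug falls into a catch-all kept under treatment policy in the primary hypothetical estimand

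*SAP*

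**What the plan says.** Protocol Section 3 states that "ICEs of interest for efficacy evaluation include treatment discontinuation, change in background therapy, and intake of prohibited medication", and the primary estimand there discards efficacy values obtained after such an event. No substances are attached to the term background therapy. Protocol 6.9 is equally general: "Participants will be required to continue on stable doses of their dyslipidemia maintenance therapy (SoC) throughout" the study.

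SAP Section 2 splits the background-therapy event in two. The non-statin part is added "to account for non-statin therapies (such as ezetimibe and bempedoic acid) when assessing the treatment effects", which is illustrative wording. SAP 3.3.1.4 then gives the operative definition of ICE 3. Under "Substances to be considered as non-prohibited background lipid lowering non-statin therapies" it has two entries, ezetimibe and bempedoic acid, and no entry for other agents.

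ICE 4 covers prohibited medication. Part (a), drugs affecting lipid parameters, has the hypothetical strategy in the primary estimand. Part (b), drugs not affecting them, has treatment policy. ICE 5 is "Any concomitant medication not explicitly specified in the above categories", with treatment policy in both efficacy columns of Table 3. SAP 4.2.1.1 repeats this for the primary estimand: "Initiation or changes in other concomitant or prohibited medication will be handled with treatment policy strategy".

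On what is prohibited, SAP 3.3.1.4 points to protocol Section 5 and the Protocol Deviation Plan, and identifies intake from a substance list in the Prohibited Medication Memo. SAP 4.1.8.1 cites protocol Sections 5 and 6.9 and the Memo, and adds: "All other concomitant medications are classified as allowed". Among lipid drugs, the protocol itself names inclisiran, other PCSK9 inhibition, lomitapide and fibrates (Section 5.2; for fibrates also 6.9, "Fibrate therapy and derivatives are prohibited").

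**The concern.** The primary question in SAP 4.2.1.1 imagines that every participant adheres to non-prohibited background lipid-lowering therapy, statin and non-statin. For a non-statin lipid drug outside the two-item list and outside the prohibited list, the stated rule does the reverse: the participant can stop or start it and the later LDL-C values remain in the primary MMRM. The resulting change in LDL-C is then attributed to the randomised arm.

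The SAP's own reasoning does not cover this case. It justifies treatment policy for ICE 4(b) on the ground that those drugs do not interfere with the efficacy endpoints. ICE 5 receives the same strategy without that condition.

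The same definitions govern the hypothetical-strategy analyses of the ten other lipid and inflammatory endpoints (SAP 4.2.3). They also govern the before/after-event split used for imputation. SAP 4.2.2.3 equates the protocol's intercurrent events with ICE 1, 2, 3 and 4(a), so a change in any other background lipid drug would not count as an event in Appendix A.

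**Working it through.** **Tracing the rule.** Take a non-statin lipid-lowering drug that is neither ezetimibe nor bempedoic acid and is on no prohibited list.

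| Category | Applies? | Reason |
|---|---|---|
| ICE 2 | No | Not a statin |
| ICE 3 | No | Not one of the two listed substances |
| ICE 4(a) or 4(b) | No | Not prohibited |
| ICE 5 | Yes | Residual category; treatment policy |

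If a participant enters on such a drug and stops it at Week 6, the protocol's text makes that a change in background therapy, and the Week 8 and Week 12 values are dropped. Under the SAP they are kept. If the drug is on the Memo's or the Deviation Plan's list, starting it is ICE 4(a), the later values are dropped, and there is no gap for that start.

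**The plan's own figures.** Protocol 9.2 gives about 375 randomised for about 320 evaluable at about 15% discontinuation. 320 / 0.85 = 376.5, so 377, which agrees with 375. In reverse, 75 × 0.85 = 63.75, or about 64 per arm. The power statement cannot be reproduced because the difference and SD are redacted. With 64 per arm and two-sided alpha 0.05, 90% power corresponds to a standardised difference of (1.960 + 1.282) × √(2/64) = 0.573.

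**Effect of leaving the values in.** The documents give no usage rates and no drug effect, so every input here is assumed. Shift in the treatment difference = (share affected on placebo − share affected on active) × drug effect, for an effect of 10 to 20 percentage points.

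| Placebo share | Active share | Shift (points) |
|---|---|---|
| 2% | 2% | 0 |
| 3% | 1% | 0.2 to 0.4 |
| 5% | 1% | 0.4 to 0.8 |
| 10% | 2% | 0.8 to 1.6 |
| 1% | 5% | −0.4 to −0.8 |

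For drugs that are started, a positive shift moves the difference toward zero and a negative one away from it. For drugs that are stopped, the directions reverse.

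Equal use still matters slightly if effects multiply: attenuation = rate × drug effect × fractional AZD0780 reduction. With an assumed drug effect of 15 to 20 points and an assumed reduction of 0.3 to 0.5, this runs from 0.03 × 15 × 0.3 = 0.14 to 0.05 × 20 × 0.5 = 0.50 points.

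**Effect of taking the values out.** If a fraction f of each arm loses its Week 12 value, n = 64 × (1 − f) and power = Φ(0.573 × √(n/2) − 1.960).

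| f | n per arm | Power |
|---|---|---|
| 0 | 64 | 90% |
| 1% | 63.4 | 89.7% |
| 3% | 62.1 | 89.1% |
| 5% | 60.8 | 88.5% |
| 10% | 57.6 | 86.8% |

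This is a worst case, since the MMRM still uses those participants' earlier visits.

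**The case against.** The strongest reply is that the categories may already be complete. ICE 3 is headed as non-prohibited therapy and names two agents. ICE 4(a) takes prohibited drugs that affect lipids. One natural reading is that every other non-statin lipid drug is on the prohibited list. A reader might infer that the Memo cannot help, because only protocol Section 5 defines what is prohibited. The SAP does not support that: 3.3.1.4 gives the Protocol Deviation Plan defining force as well, and identifies intake from the Memo's list. This part of the objection stands and makes the point conditional. It does not remove it, because the plan nowhere states that the lists cover all remaining lipid drugs.

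Second, a reader might infer that participants are free to start or stop such drugs. The protocol says otherwise. Inclusion criterion 5 requires that no medication or dose change be planned, 6.9 requires stable maintenance therapy, and other concomitant medication is considered case by case with the Study Clinical Lead. Events should be uncommon. The stability rules apply equally to ezetimibe, however, and the SAP still defines an event for it.

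Third, the catch-all is disclosed in SAP Section 2, and the primary question allows for additional treatment. That is true, but Section 2 does not disclose that its examples become a closed list. The additional-treatment clause also sits awkwardly beside the adherence clause in the same sentence.

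Fourth, starting a new drug is not plainly a change in background therapy as the protocol puts it. But ICE 3 already counts initiation of its two listed drugs, so consistency argues for treating others alike.

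**Conclusion.** The point holds as a conditional gap in a definition. On its text, the SAP narrows the protocol's event to two non-statin substances and sends any other unprohibited lipid-lowering drug to treatment policy in an estimand meant to exclude such influences. It applies only to drugs that the Deviation Plan and Memo do not list.

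The documents do not support the stronger conclusion that the primary LDL-C result is materially biased or that efficacy would be overstated. No usage data are given. Under the assumptions shown, the shift is 0 to about 1.6 percentage points, the upper end needs 10% against 2% use, and the direction depends on which arm is affected and on whether drugs are started or stopped. The effect on LDL-C is probably small. The correction is still worth making: it gives the protocol's handling whatever the unseen lists contain, and it costs little.

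**What to change.** Before unblinding, do one of the following in SAP 3.3.1.4 and Table 3:

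- Make ICE 3 open: initiation, change or discontinuation of any non-prohibited lipid-lowering non-statin drug, with ezetimibe and bempedoic acid as examples.
- Split ICE 5 as ICE 4 is split: (a) affecting lipid parameters, hypothetical strategy in the primary estimand; (b) not affecting lipid parameters, treatment policy.

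Settle the substance list in a blinded review of the coded medications, reconciled with the Prohibited Medication Memo and the Protocol Deviation Plan. Recorded medication includes over-the-counter products, vitamins and herbal supplements (protocol 6.9), so the review should keep products with negligible lipid effect from triggering exclusion of data.

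Carry the definition through Section 2, Table 3, 4.2.1.1, 4.2.2.3, 4.2.3.1 and Appendix A. If ICE 5 is split, part (a) must join the list of events in 4.2.2.3.

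The cost is wording, one review and one flag, since medications are already coded in WHODrug and summarised by ATC class. A few post-event values may leave the primary analysis. At 1% to 5% of Week 12 values the worst-case power loss is 0.3 to 1.5 percentage points from 90%.

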3.3.1.5 Definition of study treatment

Study treatment is defined as the randomly assigned study treatment. For details regarding the background lipid lowering statin therapy please refer to Section 5.1 and Appendix F of the latest approved CSP and the Statin eligibility memo.

The study treatment is dispensed in 3 bottles as represented in [Table 4](#). The participant is instructed to take 1 tablet/bottle/day. Treatment compliance is defined in Section [4.1.9](#).

Table 4 – Representation of the Drug Dispensing Scheme

	Bottle A	Bottle B	Bottle C
1 mg	AZD0780 1 mg	Placebo	Placebo
3 mg	AZD0780 1 mg	AZD0780 1 mg	AZD0780 1 mg
10 mg	AZD0780 5 mg	AZD0780 5 mg	Placebo
30 mg	AZD0780 20 mg	AZD0780 5 mg	AZD0780 5 mg
Placebo	Placebo	Placebo	Placebo

3.3.1.6 Imputation of incomplete dates

For imputations of incomplete dates the latest recommendations of the PhUSE Working Group will be followed.

If date of first administration of study treatment is missing, incomplete AE and CM start and end dates will not be imputed.

Imputation of date of first dose of study treatment

Date and time of first dose of study treatment are mandatory eCRF fields recorded in the Study Treatment Log (EXL). No imputations are expected. In the rare cases of missing date, the date of first dose of study treatment will be imputed if both the following criteria are met:

- There is at least one tablet (including kit number) recorded in the eCRF EXL form
- The first recorded tablet has a missing or partial missing date.

If that is the case, the date of first dose of study treatment is imputed with the date of eCRF Visit 2 (Day 1). Completely missing time and time where only hour is missing is imputed to 00:00. If only minutes are missing, it will be imputed to HH:00.

Imputation of date of last dose of study treatment

Date of last dose of study treatment are mandatory eCRF fields recorded in the Study Treatment Log (EXL). No imputations are expected. In the rare cases of missing date, the date of last dose of study treatment is imputed if both the following criteria are met:

- There is at least one tablet (including kit number) recorded in the eCRF EXL
- The last recorded dose has a missing or partial missing date

If that is the case, the date of last dose of study treatment is imputed with the date in which the participant ended the treatment phase recorded in the End of Treatment (EOT) eCRF.

Imputation of AE end date

The imputation of dates is used to decide the study period the AE falls into. The imputed dates should not be used to calculate durations.

Completely missing AE end dates are not imputed. Partial missing AE end dates are handled as below:

- AE is ongoing

- Set the end date as missing.
- AE is not ongoing
 - Only the day is missing: impute last day of the month of data collection.
 - Check whether end of study date or date of death is earlier than imputed AE end date
 - If yes, re-impute the end of study date (or the date of death if end of study date is missing and the participant is known to have died)
 - Both the day and the month are missing:
 - Impute 31-DEC of year of collection
 - Check whether end of study date or date of death is earlier than imputed AE end date
 - If yes, re-impute the end of study date (or the date of death if end of study date is missing and the participant is known to have died)
 - Only month is missing
 - Apply the same rules as in case of missing month and day.

Imputation of AE start date

Before proceeding with the AE start date imputation, the first dose of study treatment and the AE end date are imputed as described in the previous section.

Only partial AE start dates are imputed; Dates which are completely missing are not imputed.

Partial dates are imputed as described below:

If the day is missing and the month and/or the year is different from the month and year of the first dose of study treatment, assume 01-MMM-YYYY. If the month and year are the same as the first dose of study treatment month and year and the end date is on or after (including ongoing / missing) the first dose of study treatment, then assume the date of the first dose of study treatment. If the month and year are the same as the first dose of study treatment month and year and the end date is prior to the first dose of study treatment, then assume the end date.

If the month is missing and the year is different from the year of first dose of study treatment, assume 01-JAN-YYYY of the collected year. If the year is the same as the first dose of study treatment year and the end date is on or after (including ongoing / missing) the first dose of study treatment, then assume the date of the first dose of study treatment. If the year is the same as the first dose of study treatment and the end date is prior to the first dose of study treatment, then assume the end date.

Imputation of concomitant medications and concomitant procedures end date

The imputation of dates is used to decide if a medication or procedure is concomitant. The imputed dates should not be used to calculate durations.

Completely missing end dates or dates for which the year is missing are not imputed. Partial missing concomitant medication end dates are handled as below:

- CM is ongoing
 - Set the end date as missing.
- CM is not ongoing
 - Only the day is missing: impute last day of the month of data collection.
 - Check whether end of study date or date of death is earlier than imputed CM end date
 - If yes, re-impute the end of study date (or the date of death if end of study date is missing and the participant is known to have died)
 - Both the day and the month are missing:
 - Impute 31-DEC of year of collection
 - Check whether end of study date or date of death is earlier than imputed CM end date
 - If yes, re-impute the end of study date (or the date of death if end of study date is missing and the participant is known to have died)
 - Only month is missing
 - Apply the same rules as in case of missing month and day.

Imputation of concomitant medication and concomitant procedures start date

Both completely missing and partially missing start dates are not imputed.

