#### **8.3.1 Time Period and Frequency for Collecting AE and SAE Information**

Adverse Events will be collected from time of first dose, throughout the treatment period, and including the follow-up period.

Serious Adverse Events will be recorded from the time of signing of the ICF.

If the investigator becomes aware of an SAE with a suspected causal relationship to the IMP that occurs after the end of the clinical study in a treated participant, the investigator shall, without undue delay, report the SAE to the Sponsor.

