4.6 Safety Analyses

The domain safety covers exposure, adverse events, clinical laboratory, vital signs, and ECG.

Tables are provided for the SAS unless otherwise specified, for baseline, on-treatment and on-study periods as defined in Section 3.3.1.3.

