4.6.2 Adverse Events

4.6.2.1 Definitions and Derivations

The Medical Dictionary for Regulatory Activities (MedDRA) (latest version) is used to code the AEs. AEs are graded according to their intensity (Mild, Moderate, Severe) and they will be classified by MedDRA system organ class (SOC) and MedDRA preferred term (PT).

For rules on missing or partial dates, see Section 3.3.1. AEs with a missing start time (or where time is not collected) which occur on the same day as first study treatment administration are reported as on-treatment.

The following definitions and principles are to be followed:

Any AE

Defined as participants with at least one reported AE with an onset date within the analysis periods defined in Section 3.3.1.3.

AEs with Outcome Death

Defined as an AE with reported outcome as ‘Fatal’, there may be more than one AE with outcome death for a participant. The start date of the AE determines the analysis period, irrespective of date of death.

AEs Leading to Discontinuation of study treatment

Defined as an AE with action taken study treatment reported as drug withdrawn. The start date of the AE determines the analysis period, irrespective of date of discontinuation of study treatment.

AEs Leading to Interruption of study treatment

Defined as an AE with action taken study treatment reported as drug interrupted. The start date of the AE determines the analysis period, irrespective of date of interruption of study treatment.

AEs Leading to Withdrawal of the Participant from the Study

Defined as an AE with action taken as Participant Withdrawn from Study. The onset date of the AE determines the analysis period, irrespective of date of withdrawal.

SAEs

Defined as participants with at least one reported serious AE, irrespective of outcome, with an onset date within the defined analysis period. The onset date of the premeditating AE determines whether the SAE belongs to the analysis period, irrespective of the date the AE becomes serious.

AEs Possibly Related to study treatment

Defined as an AE that is reported as “reasonable possibility of a causal relationship between the study treatment and the AE”. If this causality evaluation is missing, it will be counted as an AE possibly related to study treatment.

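### An adverse event with no start date at all is assigned to no analysis period, so the SAP followed literally leaves it out of the AE summary tables

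*SAP*

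**What the plan says.** SAP 3.3.1.6 gives detailed rules for partial AE start dates and then excludes wholly missing ones: "Only partial AE start dates are imputed; Dates which are completely missing are not imputed".

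SAP 3.3.1.3 fixes the order of operations: "The allocation to the study periods is performed after the imputation of date as in Section 3.3.1.6". SAP 4.6 organises the safety output by period: "Tables are provided for the SAS unless otherwise specified, for baseline, on-treatment and on-study periods as defined in Section 3.3.1.3".

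The counting definitions in SAP 4.6.2.1 depend on onset:

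- Any AE: "Defined as participants with at least one reported AE with an onset date within the analysis periods defined in Section 3.3.1.3".
- SAEs: at least one serious event "with an onset date within the defined analysis period".
- Fatal AEs: "The start date of the AE determines the analysis period, irrespective of date of death". AEs leading to discontinuation, interruption or withdrawal have parallel wording.
- AEs possibly related to treatment have no date condition of their own, but their tables fall under the general by-period rule of SAP 4.6.

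For missing dates, SAP 4.6.2.1 points back to SAP 3.3.1. The only default it adds concerns the clock time on a known day: "AEs with a missing start time (or where time is not collected) which occur on the same day as first study treatment administration" count as on-treatment.

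On collection, Protocol 8.3.1 says: "Adverse Events will be collected from time of first dose, throughout the treatment period, and including the follow-up period". The same section has SAEs recorded from signature of the consent form.

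**The concern.** Each rule is reasonable alone, but together they leave a hole. An event with an unknown start date reaches period allocation without a date, so no period can contain it, and the AE summaries are built by period.

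The effect runs one way: an event can be lost from a count but never added. This applies even when other information shows that the event happened on study, such as a recorded end date after first dose, a known date of death, or withdrawal of study drug as the action taken. No planned table reports how many events were left out, so a reader of the summaries could not tell whether it mattered.

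Protocol 9.2 says that safety and tolerability drive the sample size, so complete AE counts matter to the study's stated purpose.

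**Working it through.** The plan states no figure on this point, so there is none to reproduce. The check applies the SAP rules in order and then sizes the effect.

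**1. Rule trace.** Assume first dose on Day 1, last dose on Day 84 and end of study on Day 99. By SAP 3.3.1.3 the on-treatment period ends at min(84 + 10, 99) = Day 94, and the on-study period ends at Day 99.

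| AE onset | Periods |
|---|---|
| Day -5 | Screening only |
| Day 40 | On-treatment and on-study |
| Day 97 | On-study only |
| Completely missing | None |

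The last row follows because SAP 3.3.1.6 supplies no date, and neither SAP 4.6.2.1 nor the protocol supplies a period in its place.

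**2. Comparison with the SAP's other rules for missing information.**

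- Year only known (SAP 3.3.1.6): if the year equals the first-dose year and the end date is on or after first dose, ongoing or missing, the start is set to the date of first dose. The AE is counted as on-treatment.
- Day known but time missing, on the day of first dose (SAP 4.6.2.1): counted as on-treatment.
- Causality missing (SAP 4.6.2.1): counted as possibly related.
- Start date wholly missing: counted nowhere.

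Take an ongoing AE for which only the year is known, matching the first-dose year. It is counted. Remove the year and the same AE drops out of the summaries. The first three rules lean towards counting the event; the last does not.

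**3. Size.** Input: about 75 participants per arm (Protocol 6.3), all assumed treated.

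- Largest change in one arm per affected participant: 1/75 = 1.33 percentage points.
- Largest change in the pooled AZD0780 column: 1/(4 × 75) = 1/300 = 0.33 points.
- Both need a participant whose only event in that category is undated. A participant with another dated event in the category is still counted, and the change is zero.
- SAP 4.6.2.2 plans a table of non-serious AEs occurring in more than 5% of participants. If the threshold is applied per arm, which the SAP does not specify, a term in 4 participants is 4/75 = 5.33% and appears. Losing one gives 3/75 = 4.00%, and the term drops out.

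The documents give no basis for estimating how many AEs will lack a start date.

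**The case against.** **Rarity.** Start date and time are collected for each AE (Protocol 8.3.2), AEs are reviewed at every visit from first dose, SAEs are due within 24 hours with active follow-up for fatal and life-threatening cases (Protocol 8.3.9), and source data are verified (Protocol Appendix A 7). Any partial date that gives at least the year is already imputed. All of this stands and keeps the practical effect small. It does not remove the need for a rule: the first-dose date is also a mandatory field where no imputation is expected, yet SAP 3.3.1.6 writes a fallback for it.

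**Exclusion is implied, not stated.** The SAP does not say that undated AEs are dropped; that follows from the absence of any period for them. This is correct, and it is why the point concerns what happens when the rules are followed literally. The general reference in SAP 3.3.1.6 to PhUSE recommendations cannot be shown to fill the gap, since their content is not in the documents and the SAP's own sentence is specific.

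**The events are still reported.** SAP 4.6.2.2 plans a listing of all AEs, plus key-information listings for SAEs, fatal SAEs and AEs leading to discontinuation. So the loss is from counts, not from the report.

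**Stronger readings a reader might infer.**

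- *That every safety table is affected.* Exposure, laboratory, urinalysis, vital-sign and ECG outputs do not use AE start dates.
- *That the SAP contradicts Protocol 8.3.1.* That section sets when AEs are collected and says nothing about dating or tabulating them. It does imply that a correctly collected non-serious AE began at or after first dose. It implies nothing similar for SAEs, which are recorded from consent, so an undated SAE is not necessarily post-dose.
- *That the rule mainly removes events in participants lost to follow-up, outside-hospital SAEs or deaths.* Nothing in the documents shows which events will lack dates.
- *That the comparison with placebo is biased.* The rule is the same in all arms, and no differential effect is shown. AEs are summarised descriptively and not tested.

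**Conclusion.** The point holds for the AE summary tables. Under SAP 3.3.1.6, 3.3.1.3 and 4.6.2.1 taken together, an AE or SAE with a completely missing start date belongs to neither the on-treatment nor the on-study period and is left out of the summary counts. This is more than missing detail: a stated no-imputation rule combines with a stated counting rule to give a result that can only lower AE counts, and that departs from the SAP's treatment of year-only dates and missing causality.

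The expected effect is small. It is at most about 1.3 points per affected participant in an arm of 75, and nothing where that participant has another dated event in the same category. The conclusion rests on a literal reading of the SAP with no further convention in documents not available here. It is a cheap improvement to the plan, not a threat to the study's conclusions.

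**What to change.** Add one rule to SAP 3.3.1.6, for example:

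> *For period allocation only, an AE whose start date is completely missing is assigned to the date of first dose, and so to the on-treatment and on-study periods, unless its recorded or imputed end date is before first dose.*

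Add a footnote to the AE summary tables giving the number of AEs and SAEs so assigned. This extends the logic the SAP already uses for partial dates. Limiting it to period allocation keeps the assigned date out of the durations in the listings, which SAP 4.6.2.2 derives from complete dates only.

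The cost is one sentence, one programming branch and a footnote. The downside is some misclassification. Because SAEs are collected from consent, an occasional pre-dose SAE with no end date may be counted as on-treatment, and an undated event that really began in follow-up would be too. The footnote lets a reader judge how much this matters.
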